Appendix C. Quality Control and Quality Assurance

Important Protocol Deviations

Deviations from the study conduct due to emergency situations (eg, COVID-19 outbreaks), including implemented contingency measures and their impact (eg, patient discontinuation from the study, alternative procedures used to collect critical safety and/or efficacy data, etc.), will be described in the appropriate sections of the CSR as applicable.

Study Monitoring

In case of an emergency situation (eg, COVID-19 outbreaks), monitors may not be able to access the investigational centers for on-site visits in a timely manner. A remote monitoring risk mitigation plan will be utilized for sites where on-site monitoring visits are not permitted due to an increased public health risk, in accordance with IRB/IEC approval. Details will be provided in the monitoring plan.

ECG	electrocardiogram/electrocardiography
eMDPI	electronic multidose dry powder inhaler
EoTV	end of treatment visit
PEF	Morning peak expiratory flow
FEV ₁	forced expiratory volume in the first second
FSH	follicle stimulating hormone
FVC	forced vital capacity
HBsAg	hepatitis B surface antigen
HCG	Human chorionic gonadotropin
HIV	human immunodeficiency virus
HCV	hepatitis C virus
ICE	Inter-current events
ICS	inhaled corticosteroid
IMP	investigational medicinal product
ITT	intent-to-treat

Abbreviation	Term
KM	Kaplan-Meier
LABA	long-acting β_2 agonist
LS	least square
MAR	a missing at random
MDPI	multidose dry powder inhaler
MedDRA	Medical Dictionary for Regulatory Activities
MI	multiple imputations
miITT	modified intent-to-treat
MCMC	Monte Carlo Markov Chain
MMRM	mixed model for repeated measures
MNAR	missing not at random
NRS	numerical response scale
PEF	peak expiratory flow
PDAESI	protocol-defined adverse events of special interest
PP	per-protocol
R&D	Research and Development
RTSM	Trial Supply Management
SAP	statistical analysis plan
sc	subcutaneous(ly)
SD	standard deviation
SE	standard error
██████████	██████████
SI	standard international
██████████	██████████
SOC	system organ class
SOP	standard operating procedure
ULN	upper limit of normal
UN	unstructured covariance
V	visit
WHO Drug	World Health Organization Drug Dictionary

INTRODUCTION

This Statistical Analysis Plan describes the planned analysis and reporting for Teva Branded Pharmaceutical Products R&D, Inc. study TV53275-AS-20033, (a phase 2, multicenter, randomized, double-blind, placebo-controlled, parallel-group study to assess the safety, efficacy and pharmacodynamics of TEV-53275 administered subcutaneously in adult patients with persistent eosinophilic asthma), and was written in accordance with GSD_SOP_702 (Statistical Analysis Plan).

The reader of this SAP is encouraged to read the study protocol amendment 01 (Approval Date: 18 November 2021) for details on the conduct of this study, the operational aspects of clinical assessments, and the timing for completing the participation of a patient in this study.

The SAP is intended to be in agreement with the protocol, especially with regard to the primary and all secondary endpoints and their respective analyses. However, the SAP may contain more details regarding these particular points of interest, or other types of analyses (eg, other endpoints). When differences exist in descriptions or explanations provided in the study protocol and this SAP, the SAP prevails; the differences will be explained in the clinical study report.

When the study is terminated early due to futility at interim analysis or due to sponsor's strategic decision, the planned analyses may be simplified to present the necessary information for an abbreviated clinical study report (CSR). The Bayesian analysis for the primary efficacy endpoint and the statistical analyses for some of the secondary efficacy endpoints may not be conducted for the abbreviated CSR. The analysis plan will be followed where applicable.

1. STUDY ENDPOINTS

1.1. Primary and Secondary Objectives and Endpoints

The primary and secondary study objectives and endpoints are:

Objectives	Endpoints
The primary objective of the study is to evaluate the efficacy of TEV-53275 administered subcutaneously (sc) in adult patients with persistent asthma and an eosinophilic phenotype compared to placebo	The primary endpoint is the change from baseline in clinic-based standardized baseline-adjusted trough (pre-bronchodilator) morning forced expiratory volume in 1 second (FEV ₁) at week 12
A secondary objective of the study is to evaluate the efficacy of TEV-53275 compared to placebo assessed by lung function, asthma symptoms, rescue medication use, and quality of life measures	
The secondary efficacy endpoints are:
 
 overall weekly well-controlled asthma status defined by the asthma control composite score and weekly asthma control status (Yes versus No) from week 1 through 12 and overall weekly well-controlled asthma status from week 1 through 16 overall changes from baseline in the weekly average of daily morning trough (pre-rescue bronchodilator) FEV₁ as measured by a handheld device over 12 weeks from week 1 through 12 and over 16 weeks from week 1 through 16 overall changes from baseline in weekly average of rescue medication use over 12 weeks from week 1 through 12 and over 16 weeks from week 1 through 16 changes from baseline in percentage of asthma control days (no symptoms and no rescue medication use) over 12 weeks from week 1 through 12 and over 16 weeks from week 1 through 16 change from baseline in clinic-based standardized baseline-adjusted morning trough FEV₁ at week 16 proportions of patients who achieve clinic-based FEV₁ $\geq 80\%$ predicted at weeks 12, 16, and at endpoint proportions of patients who achieve forced expiratory flow at 25% to 75% of FVC (FEF₂₅₋₇₅) $\geq 70\%$ predicted at weeks 12, 16, and at endpoint time to first clinical asthma exacerbation (CAE) throughout the study changes from baseline in Asthma Control Questionnaire (ACQ-6) at weeks 12 and 16 changes from baseline in Asthma Control Test (ACT) at weeks 12 and 16 changes from baseline in Standardized Asthma Quality of Life Questionnaire (AQLQ[S]) at weeks 12 and 16 proportions of patients who achieve FEV₁:FVC (forced vital capacity) ratio ≥ 0.80 at weeks 12, 16, and at endpoint

Objectives	Endpoints

A secondary objective of the study is to evaluate the safety and tolerability of TEV-53275 administered sc in adult patients with persistent asthma and an eosinophilic phenotype compared with placebo
	
 • The secondary safety and tolerability endpoints are: • frequency of adverse events • changes from baseline in clinical laboratory test results (serum chemistry, hematology, and urinalysis) throughout the study • changes from baseline in vital signs (blood pressure, pulse rate, respiratory rate, and body temperature) throughout the study • changes from baseline in 12-lead electrocardiogram (ECG) findings throughout the study • use of concomitant medication • local tolerability • number (%) of patients who did not complete the study due to adverse events

A secondary objective of the study is to evaluate the immunogenicity of TEV-53275 administered sc in adult patients with persistent asthma and an eosinophilic phenotype
	
The immunogenicity will be assessed by measuring the development of anti-drug antibodies (ADA), and the titer and neutralizing activity of the ADA at baseline and throughout the study

1.2.

A horizontal bar chart illustrating the distribution of 1000 samples across 15 categories. The x-axis represents the number of samples, ranging from 0 to 1000. The y-axis represents the categories, labeled 1 through 15. The bars are black with white outlines. The distribution is highly right-skewed, with the top 5 categories (labeled 10, 11, 12, 13, 14) containing the vast majority of samples (approx. 850-900).

Category	Approx. Number of Samples
1	~10
2	~10
3	~10
4	~10
5	~10
6	~10
7	~10
8	~10
9	~10
10	~900
11	~900
12	~900
13	~900
14	~900
15	~900

A horizontal bar chart illustrating the distribution of 1000 samples across 100 bins. The x-axis represents the bin index, ranging from 0 to 99. The y-axis represents the frequency of samples, ranging from 0 to 10. The distribution is highly right-skewed, with the highest frequency of 10 occurring in bin 0 and the lowest frequency of 1 occurring in bin 98. The bars are black with thin white outlines.

Bin Index	Frequency
0	10
1	9
2	8
3	7
4	6
5	5
6	4
7	3
8	2
9	1
10	1
11	1
12	1
13	1
14	1
15	1
16	1
17	1
18	1
19	1
20	1
21	1
22	1
23	1
24	1
25	1
26	1
27	1
28	1
29	1
30	1
31	1
32	1
33	1
34	1
35	1
36	1
37	1
38	1
39	1
40	1
41	1
42	1
43	1
44	1
45	1
46	1
47	1
48	1
49	1
50	1
51	1
52	1
53	1
54	1
55	1
56	1
57	1
58	1
59	1
60	1
61	1
62	1
63	1
64	1
65	1
66	1
67	1
68	1
69	1
70	1
71	1
72	1
73	1
74	1
75	1
76	1
77	1
78	1
79	1
80	1
81	1
82	1
83	1
84	1
85	1
86	1
87	1
88	1
89	1
90	1
91	1
92	1
93	1
94	1
95	1
96	1
97	1
98	1
99	1

1.3. Estimand for Primary Efficacy Endpoint

1.3.1. Primary Estimand

An estimand, in general, includes 5 inter-related attributes – treatment condition, population of interest, variable (endpoint) of interest, inter-current events (ICE) along with the strategy for handling ICE, and population-level summary for the endpoint.

Treatment condition: TEV-53275 administered subcutaneously (sc) at doses of 600 mg or 1200 mg versus placebo as an add-on therapy to the patient's current stable asthma maintenance therapy.

Population of interest: Adult patients with moderate to severe asthma with an eosinophilic phenotype on asthma maintenance therapy

The primary estimand selected for the primary efficacy endpoint will assess the change from baseline in morning trough FEV₁ at week 12 due to the initially randomized treatment as actually taken ([Mallinckrodt 2013](#)) in the modified intent-to-treat (mITT) population. This estimand assesses the treatment efficacy at week 12 attributable to the initially randomized medication.

Inter-current events (ICEs) that are expected to affect the efficacy endpoint will include:

1. Instances where a patient experiences worsening of asthma or an asthma exacerbation and the patient is placed on systemic corticosteroids, or additional asthma therapy treatment. In such cases, the investigators will be instructed to encourage the patient to continue in the study and return for planned visits until study completion in order to collect safety data after additional maintenance treatments are used. However, improvement in FEV₁ would be expected as rapidly as within 1 week for placebo patients placed on ICS (Szeffler et al 1999). It has also been shown that patients placed on ICS with long acting beta-agonists can have significant improvement in serial FEV₁ measurements on the same day (Corren et al 2007, Pearlman et al 1999). In addition, improvement in FEV₁ can occur 1 day after treatment with ICS (Kerwin et al 2019). The inclusion of data after a patient receives additional maintenance medications would potentially bias the treatment response estimates due to initially randomized study medications. Therefore, for the primary analysis, the strategy to handle these ICEs will be

- to exclude observations after the use of asthma maintenance medications (regardless of availability of data obtained afterwards).
2. Confirmed moderate or severe COVID-19 infections or any serious AE due to COVID-19: Since COVID-19 is a known respiratory disease which can adversely affect lung function, the same strategy for handling such ICEs will be applied in the primary analysis. Observations that occurred after the diagnosis of COVID-19 infections will not be used in the primary analysis.

Missing data, including those as a result of ICE handling strategies, will be handled using a multiple imputation method in the Bayesian analysis, assuming a missing at random (MAR) mechanism. The population-level summaries would be the Bayesian estimates of mean changes from baseline at week 12 for the treatment groups and corresponding 95% credible intervals, as well as posterior probability of treatment effect between each of the TEV-53275 treatment groups vs placebo being greater than 0, ie:

Posterior probability (TEV-53275 dose vs placebo >0).

As a sensitivity analysis, the reference-based multiple imputation method will be used as a missing data handling method to assess the robustness of the results under a missing not at random (MNAR) mechanism.

1.3.2. Secondary Estimand

A supplementary analysis will be conducted assessing a secondary estimand in the same treatment condition and patient population. The secondary estimand will assess the primary efficacy endpoint due to the initially randomized treatment regardless of actual treatments taken or any other occurrence of ICEs in the mITT population. The supplementary analysis will repeat the primary analysis including all observations retrieved after the occurrences of ICEs in the analysis as a means of handling the ICEs. Missing data will be handled in the same manner.

More details will be in sections [Section 6.2.2](#) and [Section 6.2.4](#).

2. STUDY DESIGN

2.1. General Design

This is a multicenter, randomized, double-blind, placebo-controlled, parallel-group study to evaluate the safety and efficacy of TEV-53275 administered subcutaneously (sc) at doses of 600 mg and 1200 mg or placebo in adult patients with moderate to severe asthma with an eosinophilic phenotype.

Patients may be eligible to participate if they have a diagnosis of asthma for at least 6 months and their current asthma maintenance therapy has been stable for at least 1 month and includes 1 of the following (see Appendix F in the study protocol):

- medium or high dose inhaled corticosteroid (ICS)±another controller
- any fixed dose combination ICS (low, medium or high) with a long-acting β -adrenergic agonist (LABA)±another controller

The patient will continue on this asthma maintenance therapy throughout the treatment period [V9/end of treatment visit (EoTV)]. For patients taking once-daily inhaled treatment, it must be taken in the morning to enable trough lung function assessments. If a patient requires a change in the timing of dosing, it is allowable as long as the investigator believes there is no inherent harm in changing the timing of the dose and the patient agrees to such change.

The study will consist of 4 periods:

- screening period of up to approximately 2 weeks
- run-in period of approximately 14 days
- double-blind treatment period of 16 weeks
- follow-up period of approximately 14 weeks beginning at the end of the double-blind treatment period

Patients who meet the criteria for inclusion and none of the exclusion criteria may enter into the run-in period at (visit [V] 2) and will continue the current asthma maintenance medication. The patient's current rescue medication will be discontinued and the patient will be provided with albuterol sulfate (117 μ g per inhalation) electronic multidose dry powder inhaler (albuterol/salbutamol eMDPI) (ProAir[®] DigihalerTM¹) or equivalent albuterol/salbutamol (dry powder or aerosol formulations are acceptable) for use as needed as rescue medication to control asthma symptoms. Patients will be provided and trained on the use of an electronic diary and handheld device to measure daily FEV₁ and peak expiratory flow (PEF). During the run-in period, patients will measure FEV₁ and PEF each morning using the handheld device prior to the use of rescue medication (whenever possible) and prior to the morning dose of asthma maintenance medication(s). Patients will also record asthma (daytime or night-time) symptom score and rescue medication (number of puffs) twice daily whether used or not. Patients may be evaluated for randomization into the study after a minimum of 14±2 days after entering the run-in period.

¹ ProAir[®] DigihalerTM is a registered trademarks of Teva Pharmaceutical Industries Ltd.

[figure not shown]
The randomization visit (V3) will occur after a minimum of 14 ± 2 days after entering the run-in period. At this visit the patient's diary data should be reviewed prior to formal lung function testing, laboratory testing and the various questionnaires to ensure compliance with diary entries and to determine if lung function, symptoms and rescue medication use meet the randomization criteria. If the patient fails to meet the diary requirements, the patient will be considered a randomization failure. Further procedures for V3 will only be conducted for patients who meet the diary.

The end of study is defined as the last visit of the last patient at the follow-up visit.

The assessments and procedures performed during each study visit are detailed in Table 2 and Appendix B of the study protocol.

The study schematic diagram is presented in [Figure 1](#).

Figure 1: Overall Study Schematic Diagram

ADA=anti-drug antibody, PK=pharmacokinetics.

2.2. Randomization and Blinding

This is a randomized, double-blind, placebo-controlled, parallel-group study.

Patients who meet all of the randomization criteria will be randomly assigned to 1 of 2 treatment groups or placebo in a 1:1:1 ratio, stratified based on maintenance therapy and screening eosinophil count:

- TEV-53275 600 mg sc
- TEV-53275 1200 mg sc
- Placebo sc

ICS and low dose ICS/LABA will be stratified separately from the medium and high dose ICS/LABA (2 separate strata) and absolute eosinophil count determined at screening (300 to <400 or ≥ 400 cells/ μ L). The stratifications are:

- ICS alone (medium or high dose) or low dose ICS/LABA and eosinophil count <400 cells/uL
- ICS alone (medium or high dose) or low dose ICS/LABA and eosinophil count ≥ 400 cells/uL

- medium or high dose ICS/LABA and eosinophil count<400 cells/uL
- medium or high dose ICS/LABA and eosinophil count \geq 400 cells/uL

Patients will be randomly assigned to treatment groups by means of a computer-generated randomization list. The specifications for randomization will be under the responsibility and oversight of Teva Global Statistics.

The sponsor's clinical personnel (and delegates) involved in the study will be blinded to the identity of the IMPs until the database is locked for analysis and the IMP assignment is known. However, if a prioritized sample analysis is needed, bioanalytical and/or clinical pharmacology personnel may be unblinded.

The randomization list will be assigned to the relevant treatment groups through a qualified service provider, eg, via the Randomization and Trial Supply Management (RTSM) system. The generation of the randomization list and management of the RTSM system will be done by a qualified service provider under the oversight of the responsible function at Teva.

[figure not shown]
2.3. Data Monitoring Committee

There is no independent Data Monitoring Committee to review ongoing safety data.

Data review committees will be set up to review the planned interim analysis results, the process for which will be described in a separate document (the interim analysis charter).

2.4. Sample Size and Power Considerations

The sample size is calibrated based on simulation studies to assess the operating characteristics of the following Bayesian success criterion for the final analysis of the primary efficacy endpoint: adjusted mean change from baseline at week 12 in trough FEV₁:

With the same base assumptions (treatment effect=0.1L and SD=0.35L), the comparison between the 1200 mg treatment group vs placebo using a two-sample t-test at one-sided alpha of

² CinqAir® is a registered to Teva Pharmaceutical Industries Ltd.

15% would provide a study power of 80.6%. The statistical software East version 6.5 was used for the calculation.

2.5. Sequence of Planned Analyses

2.5.1. Planned Interim Analyses

An interim analysis is planned, when approximately 120 patients (40 patients per arm) have completed the week 8 visit or withdrawn from the study, to assess the safety data (blinded data) and early efficacy signal (unblinded data). The details are in Section 13 and the Interim Analysis Charter.

2.5.2. Final Analyses and Reporting

All final analyses identified in this SAP will be performed after the final database lock.

3. ANALYSIS SETS

3.1. Intent-to-Treat Analysis Set

The intent-to-treat (ITT) analysis set will include all randomized patients.

In the ITT analysis set, patients will be assigned to the treatment they were randomized, regardless of which treatment they actually received.

3.2. Modified Intent-to-Treat Analysis Set

The modified intent-to-treat (mITT) analysis set is a subset of the ITT analysis set including only patients who receive at least a partial dose of IMP.

The mITT analysis set will serve as the primary analysis set for efficacy analyses. In the mITT analysis set, patients will be assigned to the treatment they were randomized, regardless of which treatment they actually received.

3.3. Safety Analysis Set

The safety analysis set will include all randomized patients who receive at least 1 dose of IMP.

In the safety analysis set, patients will be assigned to the treatment they actually received regardless of which treatment they were randomized, unless otherwise specified.

The actual treatment group assignment for safety analyses is based on the actual TEV-53275 dose received by the patient:

- The patient is assigned to TEV-53275 1200 mg treatment group, if the patient received TEV-53275, and the recorded dose was > 750 mg; The patient is assigned to TEV-53275 600 mg treatment group, if the patient received TEV-53275, but the recorded dose was ≤ 750 mg;
- The patient is assigned to placebo treatment group, if patient only received placebo.

3.4. Per-Protocol Analysis Set

The per-protocol (PP) analysis set is a subset of the mITT analysis set including only patients without important protocol deviations determined to impact efficacy assessments. These important protocol deviations will be determined before unblinding for the final analysis and will be documented separately. The list will include, but are not limited to, incorrect IMP received by a patient.

The PP analysis will serve as a supportive analysis for the primary efficacy analysis as well as the secondary efficacy analysis.

3.5. Pharmacokinetic Analysis Set

The pharmacokinetic analysis set will include those patients in the safety analysis set who have at least 1 available serum concentration value.

3.6. Anti-drug Antibody Analysis Set

The ADA analysis set (for anti-TEV-53275 antibodies) will include those patients treated with TEV-53275 in the safety analysis set.

4. GENERAL ISSUES FOR DATA ANALYSIS

4.1. General

Descriptive statistics for continuous variables include count (n), mean, SD, standard error (SE), median, minimum, and maximum. In addition, for TEV-53275 concentration, percentage coefficient of variation (%CV) and geometric mean will also be calculated. Descriptive statistics for categorical variables include patient counts and percentages, and a missing category will be displayed as appropriate.

Summaries of potentially clinically significant abnormal values for clinical laboratory tests and vital signs values will include all postbaseline values (including scheduled, unscheduled, and early withdrawal visits).

4.2. Specification of Baseline Values

Unless otherwise specified, baseline value is defined as the last observed value before the administration of IMP.

The baseline for hand-held spirometry parameters and e-diary variables will be the average of the values over the 7 days preceding day of randomization.

4.3. Handling Withdrawals and Missing Data

For all variables, only the observed data from the patients will be used in the statistical analyses, ie, there is no plan to estimate missing data, unless otherwise specified.

Dates that have incomplete information (the month and year or just the year is available) will be estimated for the purpose of calculating variables that are dependent on time if necessary. Day will be estimated as the first day (01) of the month (if month and year of partial date are available) or middle (July 1) of the year (if only year is available), unless otherwise noted. The imputations for partial dates are only for calculation purpose. Original date variables will not be modified. Listings will list dates as collected.

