8.3. Adverse Events

Adverse events will be recorded from time informed consent is obtained through the end of study participation.

All adverse events will be coded using MedDRA. Each patient will be counted only once in each preferred term or SOC category for the analyses of safety. Summaries will include treatment-emergent adverse events which are defined as adverse events occurring at or after the first dose of the IMP through the end of the follow-up visit. Listings will include all adverse events recorded.

Summaries will be presented for all adverse events (overall and by severity), adverse events determined by the investigator to be related to test IMP (defined as related or with missing relationship) (overall and by severity), serious adverse events, adverse events causing drug withdrawal or discontinuation from the study, protocol-defined adverse events of special interest (PDAESI), and PDAESI require completion of suspected anaphylaxis. Adverse events with the missing flag indicating serious will be excluded from the summary of serious adverse events but included in the summary of non-serious adverse events.

Listings for deaths, serious adverse events, adverse events leading to drug withdrawn or the study discontinuation, PDAESI, and PDAESI require completion of suspected anaphylaxis. In addition, listings for MedDRA dictionary terms for adverse event descriptions and adverse event preferred terms by patient number and treatment group will be presented.

Adverse events for patients who did not meet screening criteria will be listed.

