8.11. Concomitant Medications or Therapies

Concomitant medications, treatments, or procedures will be collected up to the end of study.

All concomitant medications will be coded using the WHO Drug. The incidence of concomitant medications will be summarized using descriptive statistics by therapeutic class and preferred term. Patients are counted only once in each therapeutic class category, and only once in each

preferred term category. The concomitant medications will include all medications taken after administration of the first IMP.

Asthma medications will be summarized by the medication class separately.

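### The SAP's partial-date rule has no adverse-event exception, so some post-dose events with incomplete onset dates are placed outside the treatment-emergent window

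*SAP*

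**What the plan says.** SAP 4.3 states the rule for month-and-year dates, "Day will be estimated as the first day (01) of the month (if month and year of partial date are available"), and continues for year-only dates: "or middle (July 1) of the year (if only year is available), unless otherwise noted". It applies wherever a time-dependent variable has to be calculated. It leaves the recorded data alone: "The imputations for partial dates are only for calculation purpose", and listings show dates as collected.

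SAP 8.3 limits the summaries to treatment-emergent events, defined as "adverse events occurring at or after the first dose of the IMP through the end of the follow-up visit". For the listings it says "Listings will include all adverse events recorded". Nothing in the visible text of 8.3 sets a different convention for partial onset dates, and the section does not appear to be redacted. Protocol 9.3.1 leaves detailed imputation rules to the SAP, so 4.3 governs.

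SAP 6.3.8 calculates time to first clinical asthma exacerbation (CAE) as the event date minus the randomization date plus 1, with no provision for a partial event date.

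**The concern.** First-of-month imputation suits history dates such as time since asthma diagnosis, where SAP 5.3 invokes it and a few weeks do not matter. It does not suit a variable whose only use is to decide whether an event falls before or after a particular day. Each patient is dosed on a single occasion (Protocol section 5), so there is one cut-off date, and it is rarely the first of a month.

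At stake is the count of treatment-emergent events for a new antibody, with safety a secondary objective and, under SAP 2.3, no independent committee reviewing ongoing safety data. The month-level loss falls in the first weeks after the injection. SAP 8.3 resolves a missing causality assessment towards the drug; an ambiguous onset in the dosing month is resolved away from it.

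**Working it through.** The plan gives no figure on this point, so there is none to reproduce. The check applies the 4.3 rule to dates and compares the result with the window in 8.3.

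**Inputs from the documents.** Day 01 or 1 July (SAP 4.3); window from first dose to the follow-up visit (SAP 8.3), which is day 210 ± 5 (Protocol Table 2); planned study period Q2/2021 to Q4/2022 (Protocol synopsis).

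**Assumptions, not in the documents.** Dosing dates evenly spread over May 2021 to April 2022. Alternative: 1 April 2021 to 4 June 2022, the last dosing date that leaves 210 days before the end of 2022. True onset evenly spread over days 0 to 210. Results are shares of partial-date records, not of all adverse events.

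**Single cases**

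| Dosed | Recorded onset | Imputed | Result |
|---|---|---|---|
| 14 Sep 2021 | Sep 2021 | 1 Sep 2021 | before dosing, lost |
| 1 Sep 2021 | Sep 2021 | 1 Sep 2021 | kept |
| 14 Sep 2021 | Oct 2021 | 1 Oct 2021 | kept |
| 14 May 2021 | 2021 | 1 Jul 2021 | kept |
| 14 Sep 2021 | 2021 | 1 Jul 2021 | before dosing, lost |
| 14 Sep 2021 | 2022 | 1 Jul 2022 | after day 210 (12 Apr 2022), lost |

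**Month-year dates.** Only the dosing month matters; later months are always imputed on or after dosing. The mean number of days from dosing to month end, counting the dosing day, is (30.44 + 1)/2 = 15.7, so 15.7/211 = 7.4% of onsets fall in the dosing month (7.5% by enumerating every dosing date and onset day). Of these, 93.6% belong to patients not dosed on the 1st. Overall 0.075 × 0.936 = 7.0% are imputed before dosing. The alternative dosing window also gives 7.0%.

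**Year-only dates**

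| | May 2021 to Apr 2022 | Apr 2021 to Jun 2022 |
|---|---|---|
| Patients dosed after 1 July of their dosing year | 50.1% | 42.6% |
| Onsets in the dosing year | 71.2% | 75.6% |
| Of these, imputed before dosing | 30.7% | 24.6% |
| All year-only onsets imputed before dosing | 0.712 × 0.307 = 21.9% | 0.756 × 0.246 = 18.6% |
| Imputed after day 210 | 21.4% | 18.2% |

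The last two rows do not overlap, so 21.9 + 21.4 = 43.3%, or 18.6 + 18.2 = 36.8%, of year-only post-dose onsets leave the window.

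**Earlier onsets.** If onsets are confined to days 0 to 112 (first dosing window), the pre-dosing shares rise to 0.139 × 0.936 = 13.0% of month-year dates and 34.8% of year-only dates; 8.5% of year-only dates then land after day 210.

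**CAE time.** Patient randomized 14 September, CAE recorded only as September: 1 − 14 + 1 = −12 days, for which the SAP has no handling rule.

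**The case against.** The strongest reply is that this will rarely matter. Protocol 7.1.2 requires onset and end dates for each event. Patients are observed for at least an hour after dosing and asked about adverse events at the day 3, 14 and 28 visits; injection sites are scored on their own form, suspected anaphylaxis has its own CRF (SAP 8.5), and missing data are queried. The first weeks are where a vague date is least likely. CAE dates are tied to a medical intervention (Protocol 6.1.2), and every event stays in the listings with its date as collected. All of this stands. It limits the number of records affected but does not change what the rule does to them.

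Two stronger readings are tempting and are not supported.

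- **That added asthma medication with a partial start date escapes the intercurrent-event rule, leaving post-rescue FEV₁ in the primary analysis.** The rule in SAP 1.3.1 is "to exclude observations after the use of asthma maintenance medications (regardless of availability of data obtained afterwards"); SAP 6.2.4.2 repeats it. Neither requires the medication to start after dosing, so an earlier imputed start, read literally, excludes more values, not fewer. Nor does being classed as prior remove a drug from the rule: under SAP 5.5 and 8.11 one record can be both prior and concomitant. It is fair to answer that all patients are on maintenance therapy at entry, so the code must somehow separate added from background drugs, and a start-date test could do so wrongly. The SAP states no such test, so the effect cannot be asserted.
- **That the error always reduces the count.** Adverse events are recorded from consent. A pre-dose event with only the year known, in a patient dosed before 1 July, is imputed to 1 July and becomes treatment-emergent.

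**Conclusion.** The defect is real and small. As written, SAP 4.3 with 8.3 removes from the treatment-emergent summaries any month-year onset in the dosing month unless dosing was on the 1st. It also removes year-only onsets in the dosing year for patients dosed after 1 July, and some year-only onsets in the following year that land beyond the follow-up visit. A negative CAE time is possible under 6.3.8.

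Under evenly spread dates the pre-dosing loss is 7.0% of month-year and 18.6 to 21.9% of year-only onsets, and more if onsets cluster early. The documents give no rate of partial dates, so no number of events can be stated. Parts of the SAP are redacted, and an exception there cannot be ruled out, though none is visible where it would be expected. No effect on the primary FEV₁ analysis is established.

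**What to change.** Add to SAP 4.3, with a cross-reference in 8.3, before unblinding for the final analysis:

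- **Adverse events.** If the known part of the onset date is compatible with onset between first dose and the follow-up visit, and no stop date shows that the event ended before dosing, count it as treatment-emergent. Set the imputed onset no earlier than the first-dose date and no later than the follow-up visit.
- **CAEs.** Set an imputed event date no earlier than the randomization date, so the shortest possible time is 1 day.
- **History dates.** Keep the present rule.

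By construction, no true post-dose adverse event with a partial date is then placed before dosing or after the follow-up visit. The cost is a few sentences and a few lines of derivation code. The downside is that some true pre-dose events with vague dates and no informative stop date will be counted as treatment-emergent, which is the conservative direction for safety.
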